# Specimens:

No specimens will be collected

### 5. Human Subjects

As mentioned above, we plan to recruit a total of 64 amputee subjects with phantom limb pain, including 16 subjects for Aim 1, 18 subjects for Aim 2, and 30 subjects for Aim 3. The number of subjects was estimated based on the pilot data.

Subject recruitment/assignment

IRB NUMBER: HSC-MS-20-1032 UTHealth IRB APPROVAL DATE: 12/03/2020

The collaborating physician (Co-I, [name]) will screen patients from the outpatient clinic of TIRR Memorial Hermann Hospital. We plan to register the project on www.clinicaltrials.gov. If patients are not currently seen by [name], but are willing to participate in the project, they need to see [name] for screening and monitoring. In addition, [name] will monitor medical conditions of the patients and manage medical problems as needed. Patients will be recruited and enrolled in the project if they meet the following criteria:

Inclusion criteria: A patient who 1) has neuropathic PLP after amputation of one limb, upper or lower limb; NOTE that BreEStim has been shown to be effective for neuropathic pain management in patients after traumatic and non-traumatic spinal cord injury in recent studies(Li et al. 2016; Li et al. 2018). Therefore, we plan to recruit patients with chronic neuropathic PLP from both traumatic and non-traumatic limb amputation. 2) has chronic pain, >3 months; 3) is between 18 to 75 years of age; 4) is stable on oral pain medications at least two weeks. Patients are instructed to continue their pain medications as prescribed during the intervention period.

**Exclusion criteria:** Patients will be excluded if they 1) are currently adjusting oral pain medications for their neuropathic pain; 2) have pain, but not neuropathic, e.g., from inflammation at the incision wound of the residual limb; 3) have a pacemaker to avoid possible side effect of electrical stimulation; 4) have amputation in multiple limbs; 5) are not able to follow commands, or to give consent; 6) have asthma or other pulmonary disease; 7) are not medically stable.

# Gender will be balanced

Potential subject populations and recruitment: Subjects will be recruited from TIRR outpatient clinic.

# 6. Data Collection and Analysis

Data collection details have been described above. Data analysis is described here.

**Experiment 1** Repeated-measures two-way ANOVA tests with factors INTERVENTION (2 levels, BreEStim and EStim) and TIME (pre- and post-intervention) will be tested on dependent variables, including VAS, QST thresholds (tactile, electrical, and thermal), to determine statistical significance between two interventions. Paired t-tests will be used to compare the duration of lasting hours between two interventions. p value is set at 0.05. As observed in the pilot data, we expect that BreEStim could have central desensitization and analgesic effects on patients with phantom limb pain, but no such effect after EStim. These findings would suggest that the central desensitization effect of BreEStim could be translated to analgesic effects in patients with PLP. Furthermore, the findings of analgesic effects along with desensitization effects in patients with PLP support central sensitization as a plausible mechanism that mediates post-traumatic PLP.

Experiment 2 Similar to Exp 1, repeated-measures two-way ANOVA tests with factors INTERVENTION (2 levels, BreEStim 120 vs. 240) and TIME (pre- and post-intervention) will be tested on dependent variables, including VAS, QST thresholds (tactile, electrical, and thermal), to determine statistical significance between two interventions. Paired t-tests will be used to compare the duration of analgesic effect (lasting hours) between two interventions. p value is set at 0.05. As shown in the pilot data, we expect that BreEStim could have dose-dependent effects on the duration but not the degree of analgesic effects. These results also suggest that BreEStim could have cumulative effects if patients receive interventions repeatedly over a period of time.

In Experiment 3, Repeated-measures two-way ANOVA will be performed to determine statistical significance between two interventions. Factors include INTERVENTION (BreEStim vs. EStim) and TREATMENT (Pre- and Post-intervention, and Followup). Variables are VAS and modified VAS and QST parameters, GWB, and CES-D. It is hypothesized that the effect of pain reduction is greater in BreEStim than in EStim for amputation patients, manifested by pain reduction on VAS assessment and parallel change of increased electrical pain threshold as shown by pilot data in Experiments 3. Furthermore, pain reduction is accompanied by improvement in general well-being and mood.

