Power analysis and estimate of sample size for Experiment 1 [name] (our biostatistician consultant) has performed power analysis based on our pilot study and historical data from the literature. A two-way repeated measures ANOVA was used to determine whether any change in VAS score was due to the interaction between INTERVENTION and TIME (i.e. whether one of two interventions is more effective at reducing VAS scores). A power analysis using the G\*power computer program (Faul et al. 2007) indicated that a sample of 12 people would be needed to detect a large effect size (> 0.8) with 85% power using a repeated measures two-way ANOVA with alpha at .05, a sample of 14 people would be needed for 90% power. To account for possible subject withdrawal (10%), we plan to recruit 16 subjects. Also to reduce the experimental bias and the order effect, the order of the interventions will be randomized.

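### In Experiments 1 and 2 the planned ANOVA tests VAS and QST on raw change scores, and adjusting for the session baselines already collected would usually be more precise

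*Combined protocol and SAP*

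**What the plan says.** Section 6 (Data Collection and Analysis) makes the pre-intervention value a level of a within-patient factor in every experiment.

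- Experiment 1: "Repeated-measures two-way ANOVA tests with factors INTERVENTION (2 levels, BreEStim and EStim) and TIME (pre- and post-intervention) will be tested" on VAS and on the tactile, electrical and thermal thresholds.
- Experiment 2: "repeated-measures two-way ANOVA tests with factors INTERVENTION (2 levels, BreEStim 120 vs. 240) and TIME (pre- and post-intervention"), on the same kinds of outcome.
- Experiment 3: "Factors include INTERVENTION (BreEStim vs. EStim) and TREATMENT (Pre- and Post-intervention, and Followup"), on VAS, modified VAS, QST parameters, GWB and CES-D.

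Section 6 does not say which ANOVA term is decisive. The power paragraph for Experiment 1 (section 4.C) does so for VAS: the aim is to see "whether any change in VAS score was due to the interaction between INTERVENTION and TIME". The same paragraph states that "a sample of 12 people would be needed to detect a large effect size (> 0.8) with 85% power", and that "a sample of 14 people would be needed for 90% power", using a "repeated measures two-way ANOVA with alpha at .05".

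The outcome-measurement text in section 4.D has VAS and QST recorded immediately before each single session and 10 minutes after it. The supplied text mentions no baseline covariate. Duration of relief in Experiments 1 and 2 is compared by paired t-test and has no pre value. Modified VAS (reduction times hours) is already a derived change measure.

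**The concern.** Each patient supplies a pre and a post value under both interventions. Entering pre as a factor level means that the interaction subtracts the whole baseline difference between the two sessions from the post difference. Subtraction is the best use of the baseline only if the post difference moves one-for-one with it. If it moves less than that, part of the baseline noise is added to the treatment contrast.

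The pilot session means did differ between conditions (VAS 5.3 and 4.9 in 3 patients; 6.4 and 5.9 in 4 patients). This shows that such differences occur, but says nothing about r. With 16 and 18 patients recruited to Experiments 1 and 2, several points of power could be recovered from data already being collected.

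**Working it through.** **1. The plan's own figure.** Experiment 1 states 12 patients (85% power) and 14 (90%) for effect 0.8 and alpha 0.05, with sidedness not stated.

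- One-sided normal approximation: ((1.645 + 1.036)/0.8)² = 11.2, so 12; ((1.645 + 1.282)/0.8)² = 13.4, so 14. This is an exact match.
- One-sided noncentral t: 13 and 15.
- G*Power-type within-factor F test (f = 0.4, four measurements, correlation 0.5 assumed): 11 and 13.
- Two-sided paired t on the interaction contrast, effect 0.8: 17 and 19, which does not match.
- Withdrawal: 14/0.90 = 15.6, so 16, as stated. Conversely 16 × 0.90 = 14.4, so about 14 evaluable.

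**2. What the interaction tests.** For each patient let Dpre and Dpost be the BreEStim-minus-EStim difference before and after the session. The two-by-two interaction contrast is Dpost − Dpre. A numerical check on simulated data gave an interaction F of 10.186 and a squared paired t of 10.186.

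**3. Variance.** Assume that Dpre and Dpost have equal variance s² and correlation r.

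- Change score: 2s²(1 − r).
- Baseline-adjusted: s²(1 − r²).
- Ratio: (1 + r)(1 − r) / [2(1 − r)] = (1 + r)/2.

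The adjusted variance is never larger before the cost of estimating the slope. That cost multiplies it by about (n − 2)/(n − 3), which is 12/11 = 1.09 at n=14. The ratio at n=14 is therefore 0.60 × 12/11 = 0.655 at r=0.2 and 0.85 × 12/11 = 0.927 at r=0.7, a saving of 34.5% and 7.3%.

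**4. Power.** Two-sided alpha 0.05. Effect dz is the mean interaction contrast divided by its standard deviation. Simulation used 60,000 runs per cell, with the adjusted test on n − 2 df. The values of r are assumptions.

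| n | dz | Planned | r=0.3 | r=0.5 | r=0.7 | r=0.8 | r=0.9 |
|---|---|---|---|---|---|---|---|
| 14 | 0.8 | 79.0% | 90.4% | 86.0% | 81.3% | 79.3% | 77.3% |
| 16 | 0.8 | 84.8% | 94.3% | 91.0% | 87.3% | 85.5% | 84.0% |
| 18 | 0.8 | 89.1% | 96.8% | 94.6% | 91.5% | 90.1% | 88.4% |
| 30 | 0.8 | 98.8% | 99.9% | 99.7% | 99.4% | 99.2% | 98.9% |
| 30 | 0.5 | 75.4% | 89.7% | 84.9% | 80.6% | 77.9% | 76.3% |

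Type I error of the adjusted test, checked at r=0.4, was about 5%. No period term was included in these runs.

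**5. Limits of the table.** The n=30 rows treat one post-minus-pre contrast, whereas the interaction planned for Experiment 3 has 2 df across three levels. They indicate direction and are not the power of the planned test. The 0.5 effect is an assumption. The text supplied for this review contains no sample-size rationale for Experiment 3, so its planning effect could not be checked.

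**The case against.** The planned ANOVA is valid and conventional, and intervention order is randomised and balanced. The issue is efficiency, not bias. That stands.

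The size is unknown. With readings just before and 10 minutes after a session, pre and post share that day's pain level, so a high r is plausible in Experiments 1 and 2. At r=0.8 the gain is essentially nil, and at r=0.9 adjustment costs 79.0 − 77.3 = 1.7 points at n=14 and 84.8 − 84.0 = 0.8 at n=16. This also stands, but the possible loss is much smaller than the possible gain (90.4 − 79.0 = 11.4 points at r=0.3, n=14).

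The plan notes one amputee with a month of carry-over, which could contaminate the second-period baseline. The change score uses that same baseline, so this does not favour the planned test.

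Three stronger readings are tempting and are not supported:

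- A reader might infer that every outcome in all three experiments is affected. GWB and CES-D are analysed only in Experiment 3. Duration has no baseline, and it is the outcome that sized Experiment 2, so that stated power is untouched. Experiment 2 also expects its doses to differ in duration, not in degree of relief, so added precision on VAS does not serve its main hypothesis.
- A reader might take the large-sample ratio (1 + r)/2 and infer that 15-40% of attainable precision is discarded. That holds only for assumed r from 0.7 down to 0.2, and it ignores the cost of estimating the slope, which matters at n=14.
- A reader might infer from the 79% that the stated sample size is wrong. The documents give neither the sidedness nor the definition of the 0.8, and 12 and 14 reproduce under a one-sided reading, so that is not concluded here.

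**Conclusion.** The point holds for VAS and QST in Experiments 1 and 2, where the targeted interaction is exactly a raw change-score test. For VAS in Experiment 1 the plan names this term; for the other outcomes the interaction is taken as the intended test because the layout is the same. At dz = 0.8 and n = 14 to 16, adjustment gains about 10-11 points of power at r=0.3, 6-7 at r=0.5 and 2-3 at r=0.7. The gain is about nil at r=0.8, and there is a loss of 1-2 points at r=0.9.

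Experiment 3 (VAS, QST, GWB, CES-D) likewise uses the pre value only as a factor level. There the gain is negligible at effect 0.8 and material only for a smaller assumed effect. The algebra is firm. The size rests on an assumed r, equal pre and post variances, and reading 0.8 as the standardised interaction contrast. This is a worthwhile efficiency gain, not a flaw in validity.

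**What to change.** In section 6, make the main analysis of VAS and QST (and of GWB and CES-D in Experiment 3) a regression of the paired post difference on the paired pre difference, testing the intercept. Include a period term because order is randomised; coding sequence as ±½ keeps the intercept equal to the treatment effect averaged over the two orders. An equivalent form models the post values with patient as a fixed effect, or with both the period baseline and the patient-mean baseline. The period baseline alone, without either of these, does not match the paired regression.

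Report the adjusted difference between interventions with its 95% CI. In Experiment 3, test Post first and Followup second, and state that order in advance. Keep the planned ANOVA as a sensitivity analysis, and leave the paired t-tests on duration unchanged.

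The cost is wording only, with no new data. The slope takes one degree of freedom and inflates variance by about 9% at n=14, which is what produces the 1-2 point loss if r is about 0.9. The period term takes one further degree of freedom.

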### Specific Aim 3: to examine the long-term effect of BreEStim on neuropathic PLP

It is critical to know whether patients will tolerate electrical stimulation and the induced analgesic effect will diminish or the effect will accumulate if patients receive BreEStim repetitively over time, before it is translated into a therapeutic device. It is hypothesized that the BreEStim treatment will produce a greater analgesic effect than the convention electrical stimulation (EStim) treatment in patients after traumatic amputation over a course of 2 weeks (10 consecutive workdays). We will examine the hypothesis by comparing electrical pain threshold and effectiveness in pain reduction between BreEStim and EStim in patients after traumatic amputation of one limb. The analgesic effect will be assessed by pain reduction in visual analog scale and quantitative measurement of electrical sensation and pain thresholds. The effect on general well-being and change in pain medication will be assessed.

IRB NUMBER: HSC-MS-20-1032 UTHealth IRB APPROVAL DATE: 12/03/2020

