The long-term BreEStim treatment is expected to have some cumulative analgesic effects. However, we decide to keep the same regime of medications, because change in medications will be a confounding factor. Therefore, the subjects will be explicitly instructed to maintain the same dose and frequency of pain medications after the BreEStim treatment even if pain is improved. The collaborating investigator [name] will screen and monitor their medications. This is exploratory at this time. If the baseline pain level improves after the 2-week BreEStim treatment, a clinical trial is warranted. Change in pain medications may be explored further in the future studies.

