**Outcome measurement includes visual analogue scale (VAS) and Quantitative Sensory Testing (QST) and Hear rate variability (HRV).** The VAS method has been extensively used and validated (McCarthy et al. 2005). Using VAS to rate pain intensity has been considered a standardized measurement to evaluate effectiveness of deep brain stimulation for pain management in a multi-center study by Medtronic (Medtronic, Minneapolis, MN). These results have been reported to US Food and Drug Administration for judgment on the efficacy of pain management(Coffey 2001). In the project, we plan to use a modified VAS to quantify pain reduction. As used in our pilot study (Li et al. 2012a; Li 2013), the effect of pain reduction is characterized by duration and amount of change in pain on VAS, i.e., how much pain is reduced and how long it lasts. As such the effect of treatment is quantified by reduction×hours. The effect and the intensity of stimulation will be recorded daily during the course of treatment. For VAS, the duration of analgesic effect from the intervention will also be recorded. VAS scores will be obtained before and 10 minutes after. Post-intervention VAS will be also assessed through follow-up phone calls every 4 hours except night time (10pm – 7am). It is important to emphasize that subjects will be explicitly instructed to maintain the same pain medication regimen even if they feel that treatment have helped in pain reduction.

QST includes tactile sensation threshold (TST), electrical sensation threshold (EST), electrical pain threshold (EPT), and thermal thresholds. VAS and QST will be recorded immediately before and 10 minutes after the interventions. In this experiment, we aim to test the central de-sensitization effect of BreEStim. To standardize QST (Li et al. 2015), all thresholds will be measured only on the residual limb at 5 cm above the distal residual limb. The symmetrical site on the contralateral limb will also be localized. After the target areas are localized and marked with a marker, subjects are instructed to stay relaxed in a chair with arms and legs comfortably supported in a symmetrical position. The order of QST will be randomized and balanced across testing sites. The following measurement will be made.

UTHealth IRB APPROVAL DATE: 12/03/2020
The University of Texas
Houlth Science Conferral Houston

16

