Heart rate variability as objective outcome measurements: We have been searching for noninvasive objective pain outcome assessment. Heart rate variability has been recognized as a physiological marker for pain assessment (Appelhans and Luecken 2008; Karri et al. 2018b; Karri et al. 2019). We will follow our recent experimental procedures (Karri et al. 2018b; Karri et al. 2019) to collect 5 minutes of Heart Rate recordings before and after the interventions.

**Experiment 2** The aim of this experiment is to explore this "dose-response" effect of BreEStim, by comparing the analgesic effects of two doses of single-session BreEStim. The same BreEStim protocol in Exp 1 will be used for Exp 2. In Exp 2, only BreEStim will be used. Two doses of BreEStim (120 vs. 240 electrical stimuli) will be given at least one week apart in a randomized order. Outcome measures, including VAS, QST thresholds, will be recorded pre- and 10 minutes postintervention. Duration of analogsic effect (lasting hours) will also be recorded.

The experimental set-up will be similar to Experiments 1&2. There are two Experiment 3 different interventions - BreEStim and EStim. Each intervention consists of 240 stimuli/session (about 40-50 min/session), 1 session/day for 10 sessions (over 2 weeks, no treatment in the weekends). After a follow-up (wash-out) period of two weeks, the same subject will be treated with the other intervention with a same follow-up of 2 weeks. The intensity of stimulation will be increased gradually as patients could tolerate. Aversiveness of electrical stimulation is part of treatment strategy. During EStim, a single-pulse electrical stimulation is delivered to the forearm through surface electrodes randomly, while electrical stimulation is triggered by volitionally effortful inhalation during BreEStim as in Exp 1.

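### Experiment 3's analysis has no session term, so it cannot show whether relief accumulates or fades over the 10 daily sessions, a question that Aim 3 itself poses

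*Combined protocol and SAP*

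**What the plan says.** Specific Aim 3 calls it critical to know, before BreEStim becomes a therapeutic device, whether "the induced analgesic effect will diminish or the effect will accumulate if patients receive BreEStim repetitively over time". Its formal hypothesis is that BreEStim relieves pain more than EStim "over a course of 2 weeks (10 consecutive workdays"). The Experimental Design section adds: "The long-term BreEStim treatment is expected to have some cumulative analgesic effects". It also links further work to a shift in background pain: "If the baseline pain level improves after the 2-week BreEStim treatment, a clinical trial is warranted".

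Each intervention is given as "1 session/day for 10 sessions (over 2 weeks, no treatment in the weekends"), and each subject receives both, with a two-week wash-out and follow-up period after each.

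On measurement, the outcome text under Experimental setup says: "The effect and the intensity of stimulation will be recorded daily during the course of treatment". It also says: "VAS scores will be obtained before and 10 minutes after". Both sentences stand under Experiment 1. The set-up of Experiment 3 is described as resembling that of the first two experiments.

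Section 6 gives the Experiment 3 analysis as a two-way repeated-measures ANOVA: "Factors include INTERVENTION (BreEStim vs. EStim) and TREATMENT (Pre- and Post-intervention, and Followup"). The dependent variables are VAS, modified VAS (reduction multiplied by hours), the sensory thresholds and the two questionnaires. No session or day factor, slope or trend is described.

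**The concern.** The aim poses a question about a path over 10 sessions, and the model looks only at points before and after that path. Whether relief grows, holds or wears off with repetition decides whether repeated use is worthwhile, and the protocol says so. As planned, the data that bear on this may be collected without any stated test.

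There is a second risk. The text does not fix the time of the Post reading in Experiment 3. If it follows the 10-minute rule of Experiments 1 and 2, the Pre-Post contrast contains the acute effect of the tenth session. A positive result could then be described as cumulative when much or all of it is what a single session does. It would also say little about the baseline pain level, on which the protocol rests its case for a further trial.

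**Working it through.** There is no stated figure to reproduce, because the point concerns what the analysis can identify. The sample size of 30 was not tested.

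**1. Question against model.** There are 10 sessions per intervention (Experiment 3 set-up). The time factor has 3 levels, none of them described as falling within the course (section 6). A Pre-Post contrast uses the end of the path only.

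**2. What an end-of-course contrast can separate.** Let y_k be the VAS reduction after session k, k = 1 to 10. For simplicity, assume pain is back at its starting level before each session. The least-squares slope is Σ(k − 5.5)y_k / Σ(k − 5.5)², with denominator 82.5. The trajectories are assumed:

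| Trajectory | y_1 to y_10 | Reduction at session 10 | Slope per session |
|---|---|---|---|
| Accumulating | 0.2 to 2.0 in equal steps | 2.0 | +0.20 |
| Constant | 2.0 throughout | 2.0 | 0.00 |
| Fading | 4.0 to 2.0 in equal steps | 2.0 | −2.0/9 = −0.22 |

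The Pre-Post contrast is 2.0 in every row. Only a term that uses the sessions tells the rows apart. A path that rises from 1.0 to 3.5 by session 5 and falls back to 2.0 also ends at 2.0. Its slope is +0.09, so a straight line alone would read it as mild accumulation.

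**3. If Post is the 10-minute reading.** In the Experiment 1 pilot, one session lowered VAS by 5.3 − 3.2 = 2.1 (BreEStim) and 4.9 − 4.1 = 0.8 (EStim). The difference is 2.1 − 0.8 = 1.3 points. A contrast of that order could arise in Experiment 3 with no accumulation. It comes from 3 patients at 120 stimuli, whereas Experiment 3 uses 240, so it is an order of magnitude only.

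**4. Why the slope of raw pre-session VAS is not the remedy.** In the Experiment 2 pilot (4 patients) the effect after 240 stimuli lasted 26.1 hours on average. Weekday sessions are about 24 hours apart, so a pre-session reading can still carry the previous day's effect. Suppose the carried-over reduction is a constant r, nothing accumulates, and the effect has gone before session 1 and after the weekend (before session 6, with a Monday start). The pre-session reductions are 0, r, r, r, r, 0, r, r, r, r. The numerator is −[(1 − 5.5) + (6 − 5.5)]r = 4r, so the slope is 4r/82.5 = 0.048r per session. Over nine steps the fitted rise is 36r/82.5 = 0.44r, with no accumulation. The EStim effect lasted 2.0 hours in the Experiment 1 pilot (120 stimuli). If it leaves no carry-over, the intervention-by-session slope is also 0.048r.

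**5. The mirror image.** Under the same assumptions, with the post-session level the same each day at A below the untreated level, the within-session change is A at sessions 1 and 6 and A − r otherwise. Its slope is −0.048r, which would look like slight fading. The session model therefore has to allow for treatment on the previous day.

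**The case against.** The strongest reply is that the hypothesis actually stated for Aim 3 is BreEStim against EStim over two weeks, and that the planned ANOVA tests it. This stands. A reader might infer that Experiment 3 cannot answer its own hypothesis; the documents do not support that.

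Nor do they support reading any positive result as merely the acute effect of session 10. The 10-minute timing is written for Experiments 1 and 2 and only inferred for Experiment 3. Follow-up is a third level of the model, and a difference well into the untreated fortnight could not be an effect lasting a day or so. The text does not say when Follow-up is read, however, and the protocol expects the two-week interval to remove accumulated effects. The design figure for Experiment 3 was not visible to this review.

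A reader might also infer that the daily recordings are certainly discarded. Modified VAS is a listed variable and could be built from them. What is missing is a rule saying which sessions enter it and how they are combined, and a three-level factor still yields no trajectory.

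It is tempting to add that averaging daily readings would save subjects. The documents give no split of within-subject variance, so no gain can be stated.

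Finally, the protocol calls this part exploratory, so its remark about a further trial should not be read as a formal decision rule. Part of the sample-size section, which may hold the Experiment 3 pilot data, was also not in the text reviewed. Section 6 is nevertheless the declared analysis section, and it has no session-level analysis.

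**Conclusion.** The point holds as a gap beside a sound main comparison. The planned factors cannot separate accumulating, constant and fading relief over 10 sessions, although Aim 3 asks for this, the design section expects accumulation, and the effect is to be recorded daily. Applying the daily-recording sentence to Experiment 3 is an inference, but a firm one: daily recording over a course of treatment fits only a multi-session experiment.

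The size is one of identification rather than power: slopes of +0.20, 0.00 and −0.22 per session share one end-of-course contrast of 2.0 points, under assumed trajectories. The mixing of acute and cumulative effects is conditional on a 10-minute Post reading; the pilot difference of 1.3 points indicates its possible scale. This should be put right before the data are analysed. It does not invalidate the test of BreEStim against EStim.

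**What to change.** 1. Keep the planned ANOVA for the formal hypothesis.
2. Add a pre-specified mixed model on the daily recorded effect, once for within-session VAS change and once for reduction × hours. Include intervention, session number, their interaction, period and a random subject effect. The interaction tests whether the effect per session grows or fades differently under BreEStim. Include an indicator for treatment on the previous day (step 5 of the working), and fit session as a category in support, so that a rise followed by a fall is not missed.
3. State how reduction × hours is computed when relief is still present at the next session, since 26.1 hours exceeds the weekday interval, and how it is summarised for the ANOVA.
4. Test a shift in baseline pain separately. Compare the session 1 pre-session reading with the first pre-session reading after an untreated weekend and with the Follow-up reading. Do not use the raw pre-session slope over sessions 1 to 10 as the test of accumulation.
5. State when Post and Follow-up are read, and that Post for any cumulative claim is not the 10-minute reading.

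The cost is SAP wording and a somewhat larger analysis. No extra visits are needed, but pre-session VAS must be confirmed as part of the daily recording, because the text says only that the effect and the stimulation intensity are recorded.
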